## 10. STUDY CALENDAR

proteins, and metabolites).

A study calendar is below (Table 7).

# 10.1 Required Data for Study Screening

The following must be obtained within 28 days prior to the 1st day of treatment:

- Medical history, medication review, physical exam, vital signs, height and weight, ECOG performance status (see Appendix A)
- CBC with manual differential, blood chemistries including complete metabolic panel, phosphorus, magnesium, uric acid, LDH, TSH, creatinine kinase, lipase, triglycerides, PT/INR, PTT, hepatitis C antibody, hepatitis B surface antigen and hepatitis B core antibody. Urine studies to include a urine dipstick for blood and protein and if positive (2+ or greater for protein) a microscopic urinalysis and 24-hour urine collection (for protein).
- Serum or urine β-HCG for females of childbearing potential
- Tumor restaging (within 6 weeks). This will consist of PET/CT scans (including neck, chest, abdomen/pelvis).
- Peripheral blood sample for biomarker studies (Section 9).
- Tumor biopsy for biomarker studies (Section 9). An archival sample may be acceptable (see Section 3.1).
- 12-Lead Electrocardiogram (EKG).

# 10.2 Required Data During Study

The following must be obtained during the study:

- Medical history, medication review, physical exam, vital signs, and weight, ECOG performance status (see Appendix A)
- Toxicity assessment
- CBC with manual differential, blood chemistries including complete metabolic panel, phosphorus, magnesium. These are required at each planned study visit -- day 1 of cycles 1-4, day 1 all maintenance cycles, day 43 of maintenance cycles.
- TSH, creatinine kinase, lipase, and triglycerides, as well as urine studies to include a urinalysis (and if urine protein positive >=2+, a 24-hour urine collection to quantify proteinuria). These are required at each planned study visit -- day 1 of cycles 1-4, day 1 all maintenance cycles, day 43 of maintenance cycles. Patients do need to meet laboratory eligibility criteria on C1D1 (see section 5.2).
- Pregnancy test at screening and D1 of each cycle (for women of childbearing age only).
- Peripheral blood sample for biomarker studies will be collected for research (see Section 9)
- Tumor restaging: PET/CT scans will be performed at baseline and after 4 doses of ipilimumab monotherapy (week 12). Among ipilimumab responders, restaging scans will occur prior to ipilimumab maintenance cycle 2 (week 24), cycle 3 (week 36), cycle 5 (week 60), and cycle 7 (week 84). Among ipilimumab non-responders, restaging scans will occur after 4 cycles of ipilimumab + nivolumab combination therapy (week 24) and prior to ipilimumab maintenance cycle 2 (week 36), cycle 4 (week 60), and cycle 6 (week 84). The end-of-treatment assessment will occur 4-12 weeks after the last doses of study therapy (i.e. weeks 112-120 for patients who complete all planned study therapy). Afterwards patients will be re-imaged every 24 weeks.

# 10.3 Required at Progression or Treatment Discontinuation and Follow-Up

- Medication review, physical exam, vital signs, ECOG performance status (see Appendix A)
- Toxicity assessment
- CBC with manual differential, blood chemistries including complete metabolic panel, phosphorus, magnesium, uric acid, LDH, TSH, creatinine kinase, lipase, triglycerides. Urine studies to include a urine dipstick for blood and protein and if positive a microscopic urinalysis and 24-hour urine collection (for protein).
- Peripheral blood sample for biomarker studies at the time of progression (if feasible)
- Core-needle tumor biopsy at the time of progression (optional)
- Tumor restaging will be performed for patients in long-term follow-up who remain in remission. Patients who progress or receive other therapy for their lymphoma (for example, consolidation with transplantation or an alternative treatment) will only be followed for relapse and survival). Surveillance imaging will consist of PET/CT scans (including neck, chest, abdomen/pelvis) every 24 weeks for up to 2 years after initiation of study therapy.

DF/HCC Protocol #: 21-204 Protocol version date: v8/06 September 2023

• Patients in remission will be followed every 3 months for 2 years, then every 6 months for 3 years. Patients who progress or receive other therapy (for example consolidation with transplantation or an alternative treatment) will only be followed for relapse and survival.

• After 5 years of active follow up (for patients who remain in remission and do not receive additional treatment), patients will be followed only for relapse and survival with follow up by phone call with the patient or the local physician every 6 months for up to 5 years.

	Table 7 - Study Calendar											
	Baseline	Сус	ele 1ª	Cycle 2	Cycle 3	Cycle 4	Re- induction cycles 1-4 b	Maintenance Cycles c		ЕОТ	Follow- Up d, j	EDC Timepoints
	Day-28 to Day 0	Day 1	Day 14- 21	Day 1	Day 1	Day 1	Day 1	Day 1	Day 43	4-12 weeks from last study treatment		
					±3	days				± 7 days	±2 weeks	
Ipilimumab		X		X	X	X	(X)	X				Day 1 of induction and re-induction cycles and each maintenance cycle
Nivolumab							(X)					Day 1 of re- induction cycles
Informed consent	X											N/A
Demographics	X											Baseline
Medical history	X											Baseline
B-HCG e	X	X		X	X	X						Baseline
Urinalysis Hepatitis B and	X											Baseline
C serologies f	X											Baseline
PT/PTT/INR EKG	X X											Baseline
Concurrent Medications	X	X		X						 	X	Baseline N/A
Physical exam	X	X		X	X	X	(X)	X	X	X	X	At each study visit
Vital signs	X	X		X	X	X	(X)	X	X	X	X	At each study visit
Height	X											Baseline
Weight	X	X		X	X	X	(X)	X				Baseline, day

												1 induction and re- induction cycles and day 1 of each maintenance cycle
Performance status (Appendix A)	X	X		X	X	X	(X)	X	X	X	X	A each study visit
CBC w/diff, serum chemistry g	X	X		X	X	X	(X)	X	X	X	X	At each study visit g
TSH, creatinine kinase, lipase, triglycerides, urine dipstick for blood and protein h	Х	X		X	X	X	(X)	X	X	X	X	At each study visit h
Cheek swab/saliva sample		X										On Cycle 1 Day1
Peripheral blood collection for biomarker studies i		X		X	X		(X)	Xi	X	X		See footnote
Tumor biopsies k	$X^k$		(X) k							(X) k		See footnote
Radiologic Evaluation 	X						(X)	$X^{l}$		X	X	See footnote
Adverse Event Evaluation			X	XX								

a: Cycles 1-4 are 21 days

b: Patients who achieve an objective response after 4 cycles of ipilimumab therapy will proceed to maintenance ipilimumab treatment. Ipilimumab non-responders (who are clinically stable) will receive re-induction with ipilimumab and nivolumab.

c: Maintenance cycles are 12 weeks (84 days). (see section 5.1)

d: Follow-up evaluation. Patients will continue on treatment until disease progression, withdrawal of consent, adverse events preventing additional therapy, or completion of study therapy. After completing treatment, patients will have every 3-month visits for 2 years or until progressive disease, then every 6-month visits for 3 years. Survival follow-up will then continue to be captured every 6 months for 5 years or until participant withdrawal, death, or removal from study. Patient who receive subsequent anti-cancer therapy will be followed for relapse and survival (but will not require active follow-up and surveillance imaging on trial).

e: Pregnancy testing at screening and on D1 of each cycle (for women of childbearing age only)

- f: Consisting at a minimum of hepatitis C antibody, hepatitis B surface antigen and hepatitis B core antibody.
- g: See Sections 10.1 and 10.2. All tests will be required at screening.
- h: See Sections 10.1 and 10.2.
- i: Peripheral blood sample(s) will be collected for correlative studies per section 9
- i: See Section 10.3.
- k: All patients are required to provide a pre-treatment core needle or excisional biopsy or an archival sample provided it was obtained within 90 days of trial initiation (see section 3.1). In addition, optional core needle biopsies may be collected during cycle 1 (between day 14-21) and at the time of progression.
- l: PET/CT scans will be performed at baseline and after 4 doses of ipilimumab monotherapy (week 12). Among ipilimumab responders, restaging scans will occur prior to ipilimumab maintenance cycle 2 (week 24), cycle 3 (week 36), cycle 5 (week 60), and cycle 7 (week 84). Among ipilimumab non-responders, restaging scans will occur after 4 cycles of ipilimumab + nivolumab combination therapy (week 24) and prior to ipilimumab maintenance cycle 2 (week 36), cycle 4 (week 60), and cycle 6 (week 84).. The end-of-treatment assessment will occur 4-12 weeks after the last doses of study therapy (i.e. weeks 112-120 for patients who complete all planned study therapy). Afterwards patients will be re-imaged every 24 weeks.

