#### 5. TREATMENT PLAN

## Figure 1 Trial Schema

Patients with R/R cHL who have previously failed a PD-1 mAb will be enrolled. For details regarding dosing, see section 5.1. Study therapy is expected to be administered on an outpatient basis. Patients will receive 4 doses of ipilimumab therapy dosed every 3 weeks (12 weeks), followed by a restaging PET/CT scan. Patients achieving an objective response to ipilimumab monotherapy will receive up to 8 doses of maintenance ipilimumab dosed every 12 weeks (96 weeks), for a total of 108 weeks of study therapy. Patients with SD or PD following ipilimumab monotherapy (who are clinically stable) will receive 4 cycles of combination ipilimumab and nivolumab therapy dosed every 3 weeks (12 weeks), followed by up to 7 doses of maintenance ipilimumab dosed every 12 weeks (84 weeks), for a total of up to 108 weeks of study therapy. Patients who have progressive disease after fewer than 4 cycles of ipilimumab are eligible to proceed to combination therapy with nivolumab and ipilimumab if they are clinically stable. Therapy will be stopped sooner for unacceptable toxicity, patient withdrawal, disease progression, physician decision, or death. Patients achieving a complete response for ≥ 6 months

can elect to stop study therapy.

Patients will be evaluated with PET/CT scans at baseline and again after 4 doses of ipilimumab monotherapy (week 12) (or earlier if there is clinical concern for progression). Among ipilimumab responders, restaging scans will occur prior to ipilimumab maintenance cycle 2 (week 24), cycle 3 (week 36), cycle 5 (week 60), and cycle 7 (week 84). Among ipilimumab non-responders, restaging scans will occur after 4 cycles of ipilimumab + nivolumab combination therapy (week 24) and prior to ipilimumab maintenance cycle 2 (week 36), cycle 4 (week 60), and cycle 6 (week 84). The end-of-treatment assessment will occur 4-12 weeks after the last doses of study therapy (i.e. weeks 112-120 for patients who complete all planned study therapy). Afterwards, patients will be re-imaged every 24 weeks. Patients in CR at any time point may have CT imaging only at subsequent time points.

Toxicity will be continuously monitored and recorded using CTCAE 5 criteria, up to 30 days following the last dose of the study treatment or until resolution of toxicity to grade 1 or baseline, whichever occurs last.

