## 11.1.2 Progression-Free and Overall Survival

Overall Survival: Overall Survival (OS) is defined as the time from randomization (or registration) to death due to any cause, or censored at date last known alive.

*Progression-Free Survival*: Progression-Free Survival (PFS) is defined as the time from randomization (or registration) to the earlier of progression or death due to any cause. Participants alive without disease progression are censored at date of last disease evaluation.

*Time to Progression*: Time to Progression (TTP) is defined as the time from randomization (or registration) to progression, or censored at date of last disease evaluation for those without progression reported.

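### Section 10.3 limits post-treatment scans and visits to patients in remission, contradicting section 5, section 10.2 and Table 7, and can make PFS censoring depend on response status

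*Combined protocol and SAP*

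**What the plan says.** Section 10.3 names two post-treatment groups.

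- Patients in remission. For scans: "Tumor restaging will be performed for patients in long-term follow-up who remain in remission", with surveillance imaging "every 24 weeks for up to 2 years after initiation of study therapy". For visits: "Patients in remission will be followed every 3 months for 2 years, then every 6 months for 3 years".
- Everyone else it mentions: "Patients who progress or receive other therapy (for example consolidation with transplantation or an alternative treatment) will only be followed for relapse and survival".

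Other current text describes the same period without a remission condition.

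- Section 5, after the EOT assessment: "Afterwards, patients will be re-imaged every 24 weeks".
- Section 10.2, repeated in Table 7 footnote l: "Afterwards patients will be re-imaged every 24 weeks".
- Table 7 footnote d: "After completing treatment, patients will have every 3-month visits for 2 years or until progressive disease".

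The Follow-Up column of Table 7 carries both footnote d and a pointer to section 10.3. Section 11.1 adds unscheduled assessment when progression is suspected and at withdrawal from treatment. Section 11.1.2 sets the PFS rule: "Participants alive without disease progression are censored at date of last disease evaluation". Section 13.4 instead ends PFS follow-up at last follow-up.

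**The concern.** The protocol does not define remission, and Appendix C classifies response as CR, PR, SD, PD or indeterminate. On ordinary usage stable disease is not remission. A patient who stops for toxicity or by choice while in stable disease, with no new lymphoma therapy, has neither remitted, progressed nor switched treatment. Section 10.3 therefore gives that patient no scans and no visits, while section 5, section 10.2 and the footnotes give both. A site reading the Follow-Up column of Table 7 is sent to both instructions.

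PFS by Lugano and by LYRIC is a secondary endpoint, to be estimated by Kaplan-Meier with 95% intervals. Kaplan-Meier assumes that patients censored at a given time have the same later risk as those still observed. Under 10.3, observation would continue or stop according to response. If unprogressed patients in stable disease do worse than responders, removing them early pushes the PFS curve up.

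**Working it through.** **1. The plan's own figure.** Section 13.3 rejects a 10% ORR if at least 4 of 13 patients respond. Exact binomial: P(X ≥ 4 | 13, 0.10) = 0.0342 and P(X ≥ 4 | 13, 0.40) = 0.8314. These reproduce the stated 0.034 and 0.83, and this point changes neither. PFS has no stated power or precision figure.

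**2. The instructions side by side, for a patient off treatment with no new lymphoma therapy.**

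| Patient | Section 10.3 | Section 5, 10.2, footnotes d and l |
|---|---|---|
| In response | Scans every 24 weeks to 2 years from start; visits | Scans every 24 weeks, no end date; visits |
| Progressed | Relapse and survival only | Footnote d visit schedule ends at progression |
| Stable disease | Not assigned | Scans every 24 weeks; visits until progression |

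The third row is the conflict. The EOT scan and assessment on suspected progression apply under either reading.

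**3. Scans at stake.** Two years is 2 × 365.25 / 7 = 104.4 weeks. The EOT scan is 4-12 weeks after the last dose. The number of 24-weekly scans that fit before the 10.3 limit is the whole part of (104 − EOT week) / 24.

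| Therapy stops, week | EOT, weeks | Scans before week 104 |
|---|---|---|
| 12 | 16-24 | 3 |
| 24 | 28-36 | 2-3 |
| 36 | 40-48 | 2 |
| 60 | 64-72 | 1 |
| 84 | 88-96 | 0 |
| 108 | 112-120 | 0 |

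The remission condition therefore costs one to three scheduled scans for stops at weeks 12 to 60. For completers the protocol puts EOT at weeks 112-120, already past the limit, and the next scan at weeks 136-144. Under 10.3 no completer gets a surveillance scan, whatever the response. Counting EOT from a final maintenance dose at week 96 gives weeks 100-108 and a next scan at weeks 124-132, so this conclusion is the same.

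**4. Size of the bias, under assumptions that are not in the protocol.** PFS is exponential. The median is 11.2 months for patients in stable disease and 15.1 months for the others (section 2.4 gives these for stable disease and partial response on nivolumab). A fraction f of patients are in stable disease; all of them stop at the month shown and, if unprogressed, are censored 2 months later. There are 200,000 simulated patients per scenario. Each cell shows true PFS, then the Kaplan-Meier estimate, then the difference in percentage points.

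| f | Stop, month | 12 months | 18 months |
|---|---|---|---|
| 15% | 3 | 0.561, 0.569, +0.8 | 0.421, 0.432, +1.1 |
| 15% | 6 | 0.564, 0.568, +0.4 | 0.422, 0.430, +0.8 |
| 15% | 9 | 0.562, 0.563, +0.1 | 0.421, 0.427, +0.6 |
| 30% | 3 | 0.544, 0.562, +1.8 | 0.404, 0.426, +2.2 |
| 30% | 6 | 0.545, 0.556, +1.1 | 0.405, 0.422, +1.7 |
| 30% | 9 | 0.546, 0.548, +0.2 | 0.405, 0.416, +1.1 |
| 50% | 3 | 0.527, 0.555, +2.8 | 0.383, 0.421, +3.8 |
| 50% | 6 | 0.530, 0.545, +1.5 | 0.385, 0.414, +2.9 |
| 50% | 9 | 0.525, 0.529, +0.4 | 0.381, 0.402, +2.1 |

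**5. How many patients.** Assume 9 re-induced patients (13 − 4, if 4 respond and all others go on). Section 2.4 cites discontinuation for adverse events of 8% with the combination, and 14% (3 of 22) stopping after one cycle of a triplet that includes brentuximab. Expected stoppers are 9 × 0.08 = 0.72 and 9 × 0.14 = 1.26, before restricting to those in stable disease. The chance of two or more is 1 − 0.92⁹ − 9(0.08)(0.92⁸) = 16%, and with 14% it is 37%.

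**The case against.** **Remission may be loose wording for not progressed.** Section 10.3 contrasts it only with progression or other therapy, and footnote d describes the same visit timetable ending at progression. That reading is possible and may be what was intended, but it is not what the words say.

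**A reader might infer that patients in stable disease get no further disease assessment.** The documents do not support this. The EOT scan has no response condition, section 11.1 requires assessment on suspected progression, and three places re-image patients without a remission condition. The defect is a contradiction, not a settled plan to stop looking.

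**A reader might infer that PFS is censored just before progression, mainly in the re-induction cohort.** The documents say neither when such patients would progress nor how common stable disease is there. Stable disease is also not a reason to stop: after re-induction, maintenance continues, with scans at weeks 36, 60 and 84. Only early stoppers who have neither responded nor progressed are affected.

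**A large effect can be constructed.** Suppose that of 9 patients 4 progress by about week 24, 2 stop in stable disease and progress by week 48, and 3 stay progression-free. Then 12-month PFS is 3/9 = 33% if all are scanned, and 5/9 = 56% if the two are censored at EOT. This is an upper-end case. It needs two such stoppers, both progressing, with scans that find it in time. The first 24-weekly scan comes 28-36 weeks after the last dose: weeks 49-57 after a last dose at week 21, and week 52 or later after one at week 24. The exact 95% intervals, 7-70% and 21-86%, largely overlap.

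**A reader might infer that a patient with Lugano progression but a LYRIC indeterminate response is also unassigned.** That patient arguably belongs to the progressed group. What stands is narrower: 10.3 does not say which criteria decide, and that group has no scheduled scan to settle LYRIC PFS.

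**Conclusion.** The contradiction over who is followed is plain in current text. If sites follow 10.3, scheduled scans for early stoppers in stable disease end at EOT and PFS censoring under section 11.1.2 depends on response status; the likely direction is upward. Reading PFS to last follow-up, as section 13.4 has it, does not cure this, because unscanned time could then count as progression-free.

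The size is unknown and probably small: about 0 to 2 patients, and 0.1 to 3 points at 12 months or 0.6 to 4 at 18 months in the scenarios above. If no patient is in this state, the bias is zero. The medians are borrowed from nivolumab-treated patients; a wider gap in prognosis between early stoppers and the rest would enlarge the effect. These are also large-sample averages, and in a cohort of 9 one patient is 11 points. PFS here is secondary and descriptive, and the primary ORR test stands. The point justifies a wording correction, not a change of design.

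**What to change.** In section 10.3, replace the remission condition in both sentences (scans and visits) with: patients who have not progressed and have not started other lymphoma therapy. Add one sentence stating that, for LYRIC PFS, an indeterminate response is not yet progression.

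Reconcile the 10.3 limit of two years from start of therapy with the uncapped 24-weekly re-imaging in section 5, section 10.2 and footnote l. Without this, the new wording adds no scans for patients who complete 108 weeks, because the limit (about week 104) falls before their EOT scan at weeks 112-120.

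The cost is wording in one section. Compared with 10.3, the population change means a few more scans for one or two patients, all of which the other sections already require.

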#### 11. MEASUREMENT OF EFFECT

#### 11.1 Antitumor Effect

18F-fluorodeoxyglucose (18F-FDG) Positron Emission Tomography (PET) imaging will be used in conjunction with Computerized Tomography (CT) imaging to confirm a disease assessment of CR at the end of treatment. The screening 18F-FDG PET-CT imaging will be used to determine evaluable index lesions for each patient. For 18F-FDG PET-CT, tumor background ratios and development of new sites of abnormality will be recorded.

Results of the 18F-FDG PET studies will be scored according to methods developed by the American College of Radiology Imaging Network. All centers participating in the study will use the same 18F-FDG PET methodologies and measures, to the extent possible, and one center will be designated as the central lab to be used for final interpretation of 18F-FDG PET data.

Anti-cancer activity will be assessed as specified in the Study Calendar (Section 10) or whenever disease progression is suspected (eg, symptomatic deterioration), or at the time of withdrawal from treatment (if not performed in the previous 6 weeks).

If imaging is used in disease assessment, the same imaging technique (CT) used to characterize each identified and reported lesion at baseline will be employed in post-baseline disease assessments.

Assessment of response will be made using the Lugano 2014 criteria and LyRIC (Appendix D).

All patients' files and radiologic images and pathology samples must be available for source verification and for potential peer review.

## 11.1.1 Duration of Response

Duration of overall response: The duration of overall response is measured from the time measurement criteria are met for CR or PR (whichever is first recorded) until the first date that recurrent or progressive disease is objectively documented (taking as reference for progressive disease the smallest measurements recorded since the treatment started, or death due to any cause. Participants without events reported are censored at the last disease evaluation).

Duration of overall complete response: The duration of overall CR is measured from the time measurement criteria are first met for CR until the first date that progressive disease is objectively documented, or death due to any cause. Participants without events reported are censored at the last disease evaluation.

Duration of stable disease: Stable disease is measured from the start of the treatment until the criteria for progression are met, taking as reference the smallest measurements recorded since the treatment started, including the baseline measurements.

